8.1.4.15 Lead measurements with Renamic programmer at implantation and each follow-up

The system performance, i.e. appropriate sensing and pacing is evaluated at the end of the implantation procedure and **at the end** of each follow-up by either manually or automatically triggered lead measurements. For this purpose the investigator performs the threshold tests, determines pacing impedance and painless shock impedance and performs P/R-wave amplitude measurements in all available channels (in DX leads also sensing measurements in the atrial channel). In the RA and RV the pulse width must be 0.4 ms, in the LV any pulse width can be chosen. For CRT-D patients measurement of LV pacing vectors with the Automatic LV VectorOpt feature is **mandatory**, either at Pre-hospital discharge or at time of the 3-month follow-up. Pacing polarities of the LV channel must be documented. The type of programmer is also documented.

If no manual measurements were performed during the on-site follow-up, the values which were automatically measured by the device the previous day are acceptable.

The investigator is asked to assess the sensing and pacing performance at the end of each follow-up (including storing of an IEGM snapshot): The sensing of the lead will be assessed as "adequate" (= the device sensed the current rhythm correctly) or "inadequate". In the ventricles the additional option "no intrinsic rhythm" (= patient is fully paced) is available to describe if an evaluation of sensing is not possible. In case the sensing is considered inadequate, the reason "oversensing", "undersensing", "not measurable" (= quality/content of IEGM does not allow any discrimination if senses are correct (e.g. lead dislodgement)) or "other" will be determined. The pacing of the lead will be assessed as "adequate" (=successful stimulation) or "inadequate". In case the pacing is considered inadequate, the reason for the evaluation is required. Possible options are "non-capture" (= no evidence of depolarization after pacing), "no output" (= failure to pace: impulses are generated by the device but is not transferred to the myocardium), "not measurable" (= quality/content of IEGM does not allow any discrimination if stimulation is successful) or "other".

At the end of the on-site follow-up procedure the full follow-up data set shall be provided to the sponsor and will be used for source data verification (see section 8.1.4.19).

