5.1 Descriptive analyses

CIP chapter 11.1 Statistical design, method and analytical procedures

... For continuous variables descriptive statistics (mean, standard deviation, median, minimum, maximum and quartiles) will be calculated. For nominal variables absolute and relative frequencies will be calculated based on non-missing data. Ordinal variables are described similarly as continuous data (minimum, 1. quartile, median, 3. quartile, and maximum) or by absolute and relative frequencies based on non-missing data of each category.

For illustration, see the following standard tables with and without subgroup analyses based on dummy data.

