5.6 Subgroups

CIP chapter 11.9 Specification of subgroups

For this clinical investigation there is no specification of subgroups in the sense that analyses will be repeated for subsets of the pre-specified analysis set. However, there are different analysis sets defined for the primary and secondary endpoints.

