8.2.4 Lead measurements (pacing thresh., sensing ampl., shock imp., lead imp.)

CIP chapter 8.1.4.15 Lead measurements with Renamic programmer at implantation and each follow-up

The system performance, i.e. appropriate sensing and pacing is evaluated at the end of the implantation procedure and at the end of each follow-up by either manually or automatically triggered lead measurements ...

The following "lead measurements" analyses have to be performed for implantation, Pre-Hospital Discharge, 3m follow-up, 6m follow-up, and 12m follow-up, whereby the variables labels have to be indicated, respectively.

Data file, identifier PRVISIT & patient_display_id_full	Notes	Variable name	Variable label	Variable level	Nominal values
lead_measurement	No report	PRVISIT	Visit	nominal	
  Implantation  Pre-Hospital Discharge  3m Follow-up  6m Follow-up  12m Follow-up

Lead measurements /Right Atrium (RA)

Data file PRVISIT & patient_display_id_full	Notes	Variable name	Variable label	Variable level	Nominal values
lead_measurement	descr.	DURAMNA	No RA lead measurements available	nominal	
  RA lead measurements not done  RA lead not implanted/not active
	descr.	DURAMRH	RA rhythm during sensing measurements	nominal	
  Sinus rhythm  Atrial fibrillation  Atrial flutter/other SVT  Atrial paced rhythm  Other  Unknown
	descr.	DURASA	RA sensing amplitude [mV], mean value	scale	n.a.
	descr.	DURAPT	RA pacing threshold [V]	scale	n.a.
	descr.	DURAPTPW	Pulse width for RA pacing threshold measurements [ms]	scale	n.a.
	descr.	DURAPI	RA pacing impedance [Ω]	scale	n.a.

Lead measurements / Right Ventricle (RV)

Data file PRVISIT & patient_display_id_full	Notes	Variable name	Variable label	Variable level	Nominal values
lead_measurement	descr.	DURVMNA	No RV lead measurements available	nominal	
  RV lead measurements not done  RV lead not implanted/not active

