	descr.	DURVMRH	RA rhythm during sensing measurements	nominal	
  Intrinsic – atrial conducted  Ventricular paced rhythm  Other atrial conducted  Ventricular paced rhythm  Other
	descr.	DURVSA	NEW: RV sensing amplitude [mV], mean value	scale	n.a.
	descr.	DURVPT	RV pacing threshold [V]	scale	n.a.
	descr.	DURVPTPW	Pulse width for RV pacing threshold measurement [ms]	scale	n.a.
	descr.	DURVPI	RV pacing impedance [Ω]	scale	n.a.
	descr.	DURVSI	Painless shock impedance [Ω]	scale	n.a.

Lead Measurements / Left Ventricle (LV)

Data file PRVISIT & patient_ display_id_full	Notes	Variable name	Variable label	Variable level	Nominal values
lead_ measurement	descr.	DULVMNA	No LV lead measurements available	nominal	
 ◦ LV lead measurements not done ◦ LV lead not implanted/not active
	descr.	DULVTYP	type of LV lead	nominal	
 ◦ Bipolar ◦ Quadripolar
		DULVSV	Permanently (first) programmed LV sensing vector	nominal	
 ◦ LV1 tip to LV2 ring (bipolar) ◦ LV1 tip to Can (unipolar) ◦ LV2 ring to LV3 ring ◦ LV2 ring to Can ◦ LV3 ring to LV4 ring ◦ LV3 ring to Can ◦ LV4 ring to Can
	descr.	DULPV01	Permanently programmed (first) LV pacing vector	scale	
 ◦ LV1 tip to LV2 ring ◦ LV1 tip to LV3 ring ◦ LV1 tip to LV4 ring ◦ LV1 tip to RV coil/ring ◦ LV1 tip to Can ◦ LV2 ring to LV1 tip ◦ LV2 ring to LV3 ring ◦ LV2 ring to LV4 ring ◦ LV2 ring to RV coil/ring ◦ LV2 ring to Can ◦ LV3 ring to LV1 tip ◦ LV3 ring to LV2 ring ◦ LV3 ring to LV4 ring ◦ LV3 ring to RV coil/ring ◦ LV3 ring to Can ◦ LV4 ring to LV1 tip ◦ LV4 ring to LV2 ring ◦ LV4 ring to LV3 ring ◦ LV4 ring to RV coil/ring ◦ LV4 ring to Can
	descr.	DULVSA	(first) LV sensing amplitude [mV], mean value	scale	n.a.
	descr.	DULVPT01	(first) LV pacing threshold [V]	scale	n.a.
	descr.	DULVPTPW01	Pulse width for (first) LV pacing threshold measurements [ms]	scale	n.a.
	descr.	DULVPI01	(first) LV pacing impedance [Ω]	scale	n.a.

Lead measurements for the second vector are reported in chapter 9.2.3 Usage and settings of MultiPole pacing (MPP) .

Data file patient_ display_id_full	Notes	Variable name	Variable label	Variable level	Nominal values

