		DULVPT01	(first) LV pacing threshold [V]		scale n.a.
		DULVPTPW01	Pulse width for (first) LV pacing threshold measurements [ms]		scale n.a.
		DULVPI01	(first) LV pacing impedance [Ω]		scale n.a.
		DULPV01_type_SAR	First pacing vector (New: LV1t-LV3r, LV2r-LV3r, LV2r-C, LV3r-LV1t, LV3r-C, LV4r-LV1t, LV4r-LV3r, LV4r-C)		 New vector  Old vector
data_SAR					

Data file, identifier PRVISIT & patient_display_id_full	Notes	Variable name	Variable label	Variable level	Nominal values
lead_measurement	descriptive or case listings for DUMPC=Yes	DULVPV02	Programmed second LV pacing vector	nominal	
  LV1 tip to LV2 ring  LV1 tip to LV3 ring  LV1 tip to LV4 ring  LV1 tip to RV coil  LV1 tip to ICD  LV2 ring to LV1 tip  LV2 ring to LV3 ring  LV2 ring to LV4 ring  LV2 ring to RV coil  LV2 ring to ICD  LV3 ring to LV1 tip  LV3 ring to LV2 ring  LV3 ring to LV4 ring  LV3 ring to RV coil  LV3 ring to ICD  LV4 ring to LV1 tip  LV4 ring to LV2 ring  LV4 ring to LV3 ring  LV4 ring to RV coil  LV4 ring to can
		DULVPT02	Second LV Pacing threshold [V]		scale
		DULVPTPW02	Pulse width for second LV pacing threshold measurements [ms]		scale
		DULVPI02	Second LV pacing impedance [Ω]		scale
		DULVPV02_type_SAR	Second pacing vector (New: LV1t-LV3r,LV2r-LV3r,LV2r-C,LV3r-LV1t, LV3r-C,LV4r-LV1t, LV4r-LV3r, LV4r-C)		
  New vector  Old vector
data_SAR					

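### LV pacing thresholds may be measured at any pulse width, but SAP 8.2.4 pools the voltages at each visit without linking them to pulse width

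*Protocol*

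**What the plan says.** Protocol 8.1.4.15 sets the measurement rule for implantation and every follow-up: "In the RA and RV the pulse width must be 0.4 ms, in the LV any pulse width can be chosen".

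SAP 8.2.4 lists the LV threshold in volts (DULVPT01, labelled "first) LV pacing threshold [V", cut here at the brackets) and its pulse width (DULVPTPW01, "Pulse width for (first) LV pacing threshold measurements [ms", likewise cut) as two separate scale variables, both marked for description. The section states that these "analyses have to be performed for implantation, Pre-Hospital Discharge, 3m follow-up, 6m follow-up, and 12m follow-up". SAP 5.1 defines the description: "For continuous variables descriptive statistics (mean, standard deviation, median, minimum, maximum and quartiles) will be calculated". SAP 5.6 adds that there is "no specification of subgroups in the sense that analyses will be repeated for subsets of the pre-specified analysis set".

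For patients with MultiPole Pacing, SAP 9.2.3 repeats the first-vector pair and adds a second (DULVPT02 and DULVPTPW02). There it allows either descriptive tables or case listings.

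**The concern.** A capture threshold in volts belongs to the pulse width at which it was found: the longer the pulse, the lower the voltage needed. The RA and RV rows avoid the difficulty because the protocol fixes 0.4 ms. The LV row does not. Two patients with identical leads can enter different voltages, and one patient can show a different voltage at the next visit because the width changed.

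Printing pulse width as its own row shows whether widths varied, but not which voltages go with which width. The joint distribution cannot be recovered from two marginal summaries. Only someone with patient-level data can rebuild it.

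At stake is how the LV threshold rows in the report are read. Pacing thresholds are listed as further data of interest (Protocol 7.5.1), and device performance is among the stated objectives (Protocol 7.1). A reader who sets the five visit tables next to each other could take a shift in pulse-width mix for a shift in lead performance.

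**Working it through.** **The plan's own figures.** The documents give no LV threshold, no pulse-width distribution and no strength-duration parameter, so there is nothing to reproduce on this point. The sample size (114 evaluable, 127 enrolled) rests on the primary endpoint and does not enter.

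**Inputs from the documents**
- Pulse width: 0.4 ms in RA and RV, free in the LV (Protocol 8.1.4.15).
- Visits with a separate summary: five (SAP 8.2.4).
- Planned patients with an LV channel: 15 HF-T + 52 HF-T QP = 67 (Protocol 8.2.4).

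**Assumptions, not in the documents**
- Strength-duration relation V(w) = Vr × (1 + c/w), with w the pulse width, Vr the rheobase voltage and c the chronaxie.
- c between 0.2 and 0.6 ms.
- Alternative LV width of 1.0 ms (1.5 ms as a further case).

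**Step 1: one lead, two widths.** The ratio is r = V(1.0)/V(0.4) = (1 + c/1.0)/(1 + c/0.4).

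| c (ms) | calculation | r at 1.0 ms |
|---|---|---|
| 0.2 | 1.2/1.5 | 0.80 |
| 0.4 | 1.4/2.0 | 0.70 |
| 0.6 | 1.6/2.5 | 0.64 |

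The same lead reads 20% to 36% lower at 1.0 ms. At 1.5 ms the ratio runs from 0.76 (c = 0.2) to 0.56 (c = 0.6).

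**Step 2: two visits, no true change.** Let a share s be measured at 0.4 ms and the rest at 1.0 ms, with width unrelated to threshold. The pooled mean is proportional to s + (1 − s)r. If s falls from 0.7 to 0.3:
- r = 0.80: 0.86/0.94 = 0.915, a fall of about 9%.
- r = 0.70: 0.79/0.91 = 0.868, a fall of about 13%.
- r = 0.64: 0.748/0.892 = 0.839, a fall of about 16%.

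If s is the same at both visits, the ratio is 1 and the artefact is 0%.

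**Step 3: would a 0.4 ms row alone be better?** Suppose longer pulses go to high-threshold leads. For illustration, two thirds of leads have 1.0 V at 0.4 ms; one third have 2.0 V at 0.4 ms but are tested at 1.0 ms with r = 0.70, reading 1.4 V.
- True mean at 0.4 ms: (2 × 1.0 + 2.0)/3 = 1.33 V.
- Pooled mean: (2 × 1.0 + 1.4)/3 = 1.13 V, 15% too low.
- 0.4 ms row alone: 1.00 V, 25% too low.

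If the high group is h times the rest, the single-width row is further from the truth than pooling when h − 1 > (1 − r)h, that is h > 1/r, or about 1.43 at r = 0.70. The group's share cancels. Stratifying is sound; promoting one stratum to the main result is not.

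**The case against.** The strongest reply is that little hangs on this, and most of that reply stands.

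- Pulse width is recorded with each LV threshold and summarised at the same visits with minimum, quartiles and maximum. If those show a single value, the voltage row can be read directly. A reader might infer that the LV summary is uninterpretable; the documents do not support that, because it depends on how much the width varies.
- A case listing under SAP 9.2.3 would show vector, voltage and width together for each patient.
- A reader might infer that a planned analysis over time, or of first against second vector, is spoiled. SAP 8.2.4 and 9.2.3 plan neither; they ask for separate summaries at each visit.
- A reader might infer that the Auto LV VectorOpt endpoint is touched. That endpoint consists of test times and investigator appraisals (Protocol 7.2.2.2, SAP 13.2), not threshold voltages.
- The LV lead is not an investigational device (Protocol 4.1); any commercially available model with the right connector may be used (Protocol 4.3).
- A reader might infer a bias towards low values. That longer pulses are used for high-threshold leads is plausible, but neither document says so.

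What remains is narrow. A visible spread of pulse widths warns the reader of mixing without letting the reader undo it, and SAP 8.2.4, unlike 9.2.3, has no listing option for these rows.

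**Conclusion.** The point holds as a minor reporting weakness. Where pulse widths vary, the LV threshold row of SAP 8.2.4 mixes voltages that are not on a common scale. The pooled mean and quartiles are then potentially confounded by pulse-width mix, and differences between the visit tables could come from that mix.

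The size is unknown. The calculated range, 20% to 36% per lead and about 9% to 16% between visits for a large shift in mix, rests on an assumed strength-duration relation, assumed chronaxies and assumed shares; a stable mix gives no between-visit artefact. No direction of bias can be stated.

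Only exploratory further data are concerned. SAP 5.3 treats everything outside the primary endpoint as exploratory, and SAP 8.6 and 9.6 set no hypotheses. The primary endpoint, its test and the sample size are unaffected.

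**What to change.** In SAP 8.2.4, and in 9.2.3 wherever descriptive tables are used instead of case listings:

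- Tabulate DULVPT01 (and DULVPT02) by the recorded pulse width, with all widths side by side and N for each. Do not make the 0.4 ms stratum the main result, since it may leave out high-threshold leads.
- If any change between visits is described, give it only for pairs with the same pacing vector and the same pulse width. State how many patients were left out because either one changed, since those may be the patients whose threshold moved.

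This uses variables already collected and leaves the sites' measurement and programming untouched. It costs one more table layout, a sentence reconciling it with SAP 5.6, and fewer patients per row out of the 67 CRT-D patients planned.

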8.2.5 Sensing and pacing assessment

CIP chapter 8.1.4.15 Lead measurements with Renamic programmer at implantation and each follow-up

The investigator is asked to assess the sensing and pacing performance at the end of each follow-up...

Lead Measurements / System performance RA

Data file PRVISIT & patient_ display_id_full	Notes	Variable name	Variable label	Variable level	Nominal values
lead_ measurement	descr.	DURASAAD	Adequate RA sensing	nominal	 Yes  No
	case listings for DURASAAD = No	DURASARE	Reason for inadequate RA sensing	nominal	 No intrinsic signal  Oversensing  Undersensing  Other
	descr.	DURAPCAD	Adequate RA pacing	nominal	 Yes  No
	case listings for DURAPCAD = No	DURAPCRE	Reason for inadequate RA pacing	nominal	 No overpacing possible  Exit block: no capture at maximum output  Other

Data file PRVISIT & patient_ display_id_full	Notes	Variable name	Variable label	Variable level	Nominal values
lead_ measurement	case listings for DURASARE =Other	CORASAOT	Specification of other reason for inadequate RA sensing	text	n.a.
	case listings for DURAPCRE=Other	CORAPCOT	Specification of other exit block for inadequate RA pacing	text	n.a.

Lead Measurements / System performance RV

Data file PRVISIT & patient_ display_id_full	Notes	Variable name	Variable label	Variable level	Nominal values
lead_ measurement	descr.	DURVSAAD	Adequate RV sensing	nominal	 Yes  No
	descr.	DURASARE	Reason for inadequate RV sensing	nominal	 No intrinsic signals  Oversensing  Undersensing  Other
	descr.	DURAPCAD	Adequate RV pacing	nominal	 Yes  No
	descr.	DURVPCRE	Reason for inadequate RV pacing	nominal	 No overpacing possible  Exit block: no capture at maximum output  Other

Data file PRVISIT & patient_ display_id_full	Notes	Variable name	Variable label	Variable level	Nominal values
lead_ measurement	case listings for DURVSARE=Other	CORVSAOT	Specification of other reason for inadequate RV sensing	text	n.a.
	case listings for DURVPCRE=Other	CORVPCOT	Specification of other exit block for inadequate RV pacing	text	n.a.

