Lead Measurements / System performance LV

Data file PRVISIT & patient_ display_id_full	Notes	Variable name	Variable label	Variable level	Nominal values
lead_ measurement	descr.	DULVSAAD	Adequate LV sensing	nominal	 Yes  No
	descr.	DULVSARE	Reason for inadequate LV sensing	nominal	 No intrinsic signal  Oversensing  Undersensing  Other
	descr.	DULVPCAD	Adequate LV pacing	nominal	 Yes  No
	descr.	DULVPCRE	Reason for inadequate LV pacing	nominal	 No overpacing possible  Exit block: no capture at maximum output  Other

Data file PRVISIT & patient_ display_id_full	Notes	Variable name	Variable label	Variable level	Nominal values
lead_ measurement	case listings for DULVSARE=Other	COLVSAOT	Specification of other reason for inadequate LV sensing	text	n.a.
	case listings for DULVPCRE=Other	COLVPCOT	Specification of other exit block for inadequate LV pacing	text	n.a.

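### SAP 8.2.5 has no not-evaluable level for RV and LV sensing, so a fully paced patient recorded under its codes lowers the descriptive adequacy rate without a fault

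*Protocol*

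**What the plan says.** **Protocol 8.1.4.15.** The basic assessment has two levels: "The sensing of the lead will be assessed as 'adequate' (= the device sensed the current rhythm correctly) or 'inadequate". For the ventricles there is a third: "the additional option 'no intrinsic rhythm' (= patient is fully paced) is available to describe if an evaluation of sensing is not possible". The reasons offered for an inadequate result do not include absence of intrinsic rhythm: "In case the sensing is considered inadequate, the reason 'oversensing', 'undersensing', 'not measurable", plus an *other* category. The protocol explains *not measurable* as an IEGM that does not permit a judgement and gives lead dislodgement as an example.

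**SAP 8.2.5.** This section cites Protocol 8.1.4.15. The items "Adequate RV sensing" and "Adequate LV sensing" each carry the values Yes and No only. Under "Reason for inadequate RV sensing" the levels are "No intrinsic signals", oversensing, undersensing and other. The list under "Reason for inadequate LV sensing" is the same apart from the singular form. *Not measurable* does not appear.

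**SAP 5.1.** Relative frequencies of nominal variables are based on non-missing data.

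**SAP 8.2.4.** The RV lead-measurement table records the rhythm during the sensing measurement at each visit, and one of its levels is a paced ventricular rhythm. SAP 8.2.5 does not use it.

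**The concern.** The protocol's not-evaluable state has become, in the SAP, a reason for an inadequate result. If a site records a fully paced patient as No with that reason, the adequacy percentage mixes two different things: sensing faults, and patients in whom sensing could not be judged.

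Sensing and pacing adequacy is how Protocol 8.1.4.15 has system performance evaluated at implantation and at every follow-up. Protocol 7.1 says that device performance shall be assessed and that the results will feed the clinical evaluation and regulators outside the CE region. A ventricular sensing rate below 100% with no underlying fault would be misleading in that use.

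**Working it through.** The plan states no figure for this rate, so there is nothing to reproduce. The check is a comparison of categories, followed by an illustration of size.

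**Step 1: categories for ventricular sensing.**

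| Situation | Protocol 8.1.4.15 | SAP 8.2.5 |
|---|---|---|
| Rhythm sensed correctly | adequate | Yes |
| Oversensing, undersensing, other | inadequate | No, same reasons |
| IEGM does not permit a judgement | inadequate (*not measurable*) | no matching reason |
| Fully paced, no intrinsic rhythm | separate option, not evaluable | no separate level; nearest code is No with no intrinsic signal as the reason |

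**Step 2: is a third level hidden by abbreviation?** SAP 1.3 says that value lists may be shortened and marks this with an ellipsis. The Yes/No lists for RV and LV sensing carry none.

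**Step 3: are such records removed later?** SAP 8.3 to 8.5 only refer back to the general rules in 5.4, 5.5 and 5.1. Elsewhere the SAP does set non-informative answers to missing: *Unknown* for heart-failure hospitalization and for LV lead implantation details (8.2.1), *Not done* for the AV Opt test (8.2.3), and *Not done* for several Auto LV VectorOpt items (9.2.6). There is no such rule in 8.2.5.

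**Step 4: effect on the rate.** Let n be the patients with a record, k the fully paced patients coded No, and f the true faults.

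- Protocol categories: (n − k − f) / (n − k)
- SAP categories: (n − k − f) / n

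Inputs: Protocol 8.2.4 plans 15 HF-T and 52 HF-T QP devices, so n = 15 + 52 = 67 CRT-D patients. Set f = 0 and ignore drop-outs. The documents give no value for k, so the share of fully paced patients is an assumption shown over a range.

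| Assumed share | k | Protocol categories | SAP categories |
|---|---|---|---|
| 2% | 1 | 66/66 = 100% | 66/67 = 98.5% |
| 5% | 3 | 64/64 = 100% | 64/67 = 95.5% |
| 10% | 7 | 60/60 = 100% | 60/67 = 89.6% |
| 20% | 13 | 54/54 = 100% | 54/67 = 80.6% |

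For k = 3 the exact 95% intervals are 94.4% to 100% (64/64) and 87.5% to 99.1% (64/67). If those 3 were the only fully paced patients among all 127 planned, the RV rate across device types would be 124/127 = 97.6%.

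**The case against.** **The SAP is not the form.** The eCRF is not among the documents. A site might have a third option there, or leave the item blank, in which case the record drops out as missing. The ellipsis convention is also not applied reliably: implantation type has three values in SAP 8.2.1 but two, without an ellipsis, in the wearing-comfort table of 8.2.2. This stands. It is therefore not shown that fully paced patients will be coded No. But neither document tells sites to leave the item blank, and the SAP as printed has nowhere else to put them.

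**The split can be recovered.** The reason is itself tabulated for RV and LV, and rhythm during measurement is reported too. A careful reader could separate the cases. This limits the harm but does not correct the adequacy percentage.

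**A blanket recode could hide faults.** The SAP does not define its no-intrinsic-signal code as fully paced, and the protocol's *not measurable* reason, with dislodgement as its example, is missing from the SAP list. Some real lead problems may be filed under that code. This stands, and the fix is narrowed accordingly.

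**Three stronger readings that a reader might infer are not supported.**

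- *Pacing adequacy has the same defect.* The SAP reason *No overpacing possible* is not in the protocol's list, but neither document defines it. The protocol offers no neutral option for pacing and counts *not measurable* pacing as inadequate. Excluding such records would depart from the protocol.
- *CRT-D patients are mostly affected because they are paced nearly all the time.* A high pacing percentage does not mean that intrinsic rhythm is absent. CRT AutoAdapt works by measuring intrinsic AV conduction (Protocol 4.7.1.3).
- *The rate loses comparability with the predecessor's 145 of 145 for sensing.* That result (Protocol 5.2.2) is for RV leads in a Plexa lead cohort. Here RV leads are freely selectable outside the DX systems, and no comparison is planned. The protocol does not say why 150 patients were assessed for pacing but 145 for sensing.

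**Conclusion.** The mismatch between Protocol 8.1.4.15 and SAP 8.2.5 is explicit for RV and LV sensing. As the SAP is written, a fully paced patient recorded as No for lack of an intrinsic signal lowers the adequacy rate without any fault. The bias can only be downward.

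Its size is unknown. The drop from 100% to 95.5% rests on an assumed 3 of 67 fully paced CRT-D patients, no true faults and no drop-outs; the range shown runs from 98.5% to 80.6%.

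The reach is limited. These are further data of interest (Protocol 7.5.1) without hypotheses (SAP 8.6). The primary endpoint, its test and the sample size are untouched. The protocol gives the extra option for the ventricles only, so the RA table in SAP 8.2.5 and the Plexa S DX atrial table in 10.2.2 are outside this point, although they list a similar reason.

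**What to change.** In SAP 8.2.5, for RV and LV only:

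1. Report sensing in three levels, as the protocol does: adequate, inadequate, not evaluable.
2. Class a record as not evaluable only if the reason is no intrinsic signal **and** the ventricular rhythm recorded at that visit (SAP 8.2.4) is paced. Remove it from the denominator and report the count at each visit.
3. Keep every other no-intrinsic-signal record as inadequate.
4. Restore the protocol's *not measurable* reason, counted as inadequate.
5. Leave *No overpacing possible* in the pacing denominator. Define it and reconcile it with the protocol's pacing reasons.

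Two labelling slips bear on this derivation and should be corrected in the same edit. The RV table in 8.2.5 uses the RA variable names DURASARE and DURAPCAD, while its case listing refers to DURVSARE. The rhythm item in the RV table of 8.2.4 is labelled as RA rhythm and repeats the paced level.

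The derivation needs only a few lines and uses items the SAP already lists, with no extra visits. The downside is slightly more programming and a slightly smaller denominator.
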